1.2 Study Objectives

The objectives of this study are to assess the feasibility, acceptability, and efficacy of the health insurance education program in AYA's recently diagnosed with cancer.

1.3 Study Outcomes

Primary Outcome:

Feasibility

The percent of AYA cancer patients enrolled in the study will be used as the measure of feasibility.

Acceptability

Information on acceptability of the program material and the Zoom format and what they liked or disliked about the intervention content

Satisfaction

Satisfaction with the Interpersonal Relationship with the Navigator score (PSN-I)¹⁻² will be used as the measure of acceptability. This consists of the sum of 9 items with a higher score indicating greater participant satisfaction with the relationship between themselves and the navigator. Participants will be asked these questions during the follow-up survey.

Secondary Outcome:

Efficacy

Differences in baseline and follow up response values for health insurance literacy and financial toxicity will be used to measure efficacy.

Health insurance literacy will be measured using two sections of the Health Insurance Literacy Measure (HILM)³ as well as questions concerning familiarity with provisions of the affordable care act, and laws surrounding insurance (e.g. COBRA, ADA). The sum of responses from each of these categories of questions will be used where higher scores indicate higher literacy.

Financial toxicity will be measured using the COmprehensive Score for financial Toxicity (COST)⁴. The COST score consists of 11 questions where lower scores indicate higher financial toxicity.

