Health insurance literacy is defined as a patient's ability to make informed decisions about choosing and using health insurance.¹² Cost-related literacy is a related concept that is defined as how well a patient understands financial concepts specific to cancer care and their comfort discussing financial burden with providers.^{10,13} Our studies of AYA cancer patients demonstrate that they feel uninformed about their insurance and want to have cost conversations with providers, but feel uncomfortable doing so.¹⁴ This is not surprising as AYA cancer patients tend to be healthy prior to diagnosis and therefore have little experience with the health care system and insurance.¹⁵ At the same time, the Affordable Care Act (ACA) has expanded opportunities for AYA cancer patients to obtain insurance coverage,¹⁶⁻¹⁸ but our studies demonstrate AYAs' low understanding of the ACA's provisions.^{19,20} Under the ACA, many young adults with cancer are now insured through age 26 on their parents' insurance, whereas those over age 26 have not made the same insurance coverage gains.¹⁷ However, our research demonstrates that regardless of age and insurance status, AYAs with cancer are worried about insurance and costs and want education on these issues.¹⁴

2. Purpose and Objectives

In this study, we are adapting and testing educational modules to improve AYA cancer patients' knowledge of insurance and costs.

Aim 2: Conduct a telemedicine-based pilot randomized controlled trial (RCT) of the health insurance education program (HIEP) among AYA cancer patients.

- Hypotheses: Among AYA cancer patients, the HIEP will be feasible and acceptable and improve their health insurance literacy and cost-related literacy compared to usual care.
- Intervention: Pre-intervention and post-intervention surveys will assess insurance literacy and cost literacy. The intervention will be comprised of four, 30 to 45-minute HIEP sessions which will be delivered by HIAYA Patient Navigators over the intervention period.
- Aim 2a: Determine (1) The feasibility (number of eligible enrolled/sessions completed) and (2) the acceptability (and/or satisfaction) of conducting a telemedicine-based HIEP with AYA cancer patients.
- Aim 2b: Assess the efficacy of the HIEP to improve AYAs' health insurance literacy and cost-related literacy.

Aim 3: Evaluate and refine the HIEP for dissemination in a larger RCT.

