6. Data Collection

Following written informed consent, at pre-intervention we will collect data on participants' demographics, medical history, financial status, and family history through a protected online questionnaire, by communicating in person, over the phone, or by email.

The team will use the Research Electronic Data Capture (REDCap) software application to collect and manage the data for this project. The REDCap database is on a secure server maintained by the Huntsman Cancer Institute (HCI) bioinformatics shared resource and the HCI Computer and Technology Group (CATG).

Voice recordings will be stored securely on the [name] Team drive at Huntsman Cancer Institute or on password protected computers at HCI.

7. Risks and Benefits

Questions and discussion about health insurance and medical costs can be psychologically stressful to participants, and there is the risk of loss of confidentiality and/or loss of privacy.

Participants may learn more about health insurance coverage and access. Societal benefits include greater insight of AYA cancer patients and insurance understanding.

8. Cost and Compensation

- There is no cost to be in this study
- There will be gift card compensation available for participants, ranging from \$40 to \$60 depending on procedures completed.
 - Baseline Survey completion: \$20 gift card Follow-up
 - Survey completion: \$20 gift card
 - Post-intervention session interview completion: \$20 gift

9. Statistical Methods, Data Analysis and Interpretation

9.1 Aim 2

We will use descriptive statistics to report on the following endpoints: intervention feasibility (e.g., percent of AYA cancer patients enrolled), acceptability (e.g., satisfaction) and efficacy (e.g., health insurance literacy, cost-related literacy, provider communication about cost, financial toxicity). We will run descriptive statistics to examine group differences at baseline; any imbalanced covariates will be included as adjustment variables. We will use chi-squared and independent sample t-tests to compare end-of-treatment changes in preliminary efficacy outcomes between the two groups.

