Although a 3-month post treatment follow-up period is brief, we will also conduct exploratory comparisons with other study outcomes to see if trends change in the expected direction. We will compare baseline/end-of-treatment, within groups, with paired t-tests for continuous outcomes and McNemar's tests for categorical outcomes. In addition, we will use bivariate statistics to examine demographic and cancer-related factors (type of diagnosis, age at diagnosis, treatment), and health status with feasibility, acceptability, and preliminary efficacy outcomes. Multivariate analyses, adjusting for imbalanced covariates, will be conducted in the context of linear or logistic models, potentially with random effects for patient, as appropriate. We will test for differences by sex, age, sexual orientation, and race/ethnicity in the effects. We will also conduct analyses to determine moderators of the intervention effects. Tests of interactions between covariates (moderation analyses) will be conducted in the context of both the unadjusted and adjusted versions of the regression models with effects for both the covariate of interest and the treatment arm, as well as additional covariate by covariate interaction terms.

Our primary outcomes of interest are feasibility and acceptability of the HIEP program. We expect 80 participating AYAs to enroll throughout 1 year of the pilot RCT implementation. We expect at least 72 to complete the 3 month follow-up (10% attrition rate) based on retention in our previous studies. However, for our secondary outcomes we anticipate adequate sample size to explore meaningful differences in the outcomes. For example, for financial toxicity, our

University of Utah

Protocol Version 04

Protocol No. 00127029

preliminary data show that for the 11-item COST score,⁷⁷ average scores at enrollment in the navigation program for AYAs ranges from 25.79 (standard deviation, SD=10.11) for younger AYAs to 18.22 (SD=10.81) for older AYAs. Lower COST scores indicate greater financial distress. We expect to have >80% power to detect differences in the mean improvement in the COST score between the intervention and control groups which differ by 0.67 SD based for our target N=72 completing the RCT.

9.2 Aim 3

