1.1 Study Design & Randomization

This is a multi-site behavioral intervention study. The study will be run between August 2020 and December 2021. For randomization, participants will be stratified by age at cancer diagnosis (17-26; 27-39 years) and treatment site and blocked into groups of 4 patients (2 control, 2 intervention) to ensure that control and intervention groups are approximately balanced by age and within sites. Random allocations within strata will be computer generated and automatically assign individuals to a study arm after the study coordinator determines patients' eligibility and obtains consent. All participants will then take a baseline survey and meet with the patient navigator. Participants enrolled in the intervention group will attend 4 educational sessions to learn about health insurance. Participants not enrolled in the intervention group will have access to the patient navigator for assistance, as is standard care. Participants will all take a follow-up survey. A randomly selected group of all participants will be interviewed after the follow-up survey.

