2.3.2 Analysis of Feasibility

This will be the percentage of individuals who consented to be a part of the study out of the total number of approached individuals.

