2.4.5 Center Pooling

Participants were randomized in a manner that required approximately equal enrollment of participants from each site to control for any possible center effects, further we plan on including facility as a variable in our models. As such, no additional controlling for site will be done all participants will be pooled for analyses.

3. Changes to Planned Analysis from The Protocol

The protocol analysis plan was followed; however, we did run multivariable regressions to ensure that covariates did not influence our findings. We also performed sensitivity analyses examining report of policy holder status and by site of recruitment.

4. Interim Analysis

No official interim analyses are planned

5. Statistical Analysis Software

All statistical analysis and summary information will be completed in STATA 14.0 or higher.

6. References

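### The SAP's primary feasibility measure is the consent percentage alone; it omits the sessions-completed component of protocol Aim 2a and so says nothing about whether the four-session HIEP was delivered.

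*SAP*

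**What the plan says.** Protocol section 2, Aim 2a, sets out to determine "The feasibility (number of eligible enrolled/sessions completed"), and the object of that feasibility is "conducting a telemedicine-based HIEP with AYA cancer patients". Protocol 9.1 states: "Our primary outcomes of interest are feasibility and acceptability of the HIEP program". Earlier in 9.1, and in the synopsis, the endpoint appears as "intervention feasibility (e.g., percent of AYA cancer patients enrolled"), that is, with percent enrolled as an example.

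The SAP turns the example into the definition. Section 1.3 says "The percent of AYA cancer patients enrolled in the study will be used as the measure of feasibility". Section 2.3.2 gives the calculation: "This will be the percentage of individuals who consented to be a part of the study out of the total number of approached individuals".

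From SAP 1.1 onward, the HIEP sessions appear only as procedure (1.1 and 1.5). No variable, analysis population or summary concerns attendance. SAP section 3 says "The protocol analysis plan was followed" and lists added regressions and sensitivity analyses, with no mention of feasibility.

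**The concern.** The Aim 2 hypothesis is that the HIEP will be feasible, and Aim 3 uses the pilot to refine it for a larger RCT. For that decision one needs to know whether patients in active cancer treatment attend four sessions over two months. The SAP's percentage answers a different question: how many of those approached agree to join a trial in which they have an even chance of usual care.

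A high consent percentage could then be reported as feasibility of a programme that many participants did not finish. If the efficacy comparison showed no difference, the planned analyses would not help a reader tell an ineffective programme from one that was not received.

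The protocol's own analysis plan also suggests that a participant-level feasibility measure was intended. Section 9.1 plans to relate demographic, cancer-related and health-status factors to feasibility. Among people who consented, enrolment does not vary; sessions completed does.

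**Working it through.** **The plan's own figure.** Neither document gives a target, threshold or precision for feasibility. The only design calculation is for the COST score, a secondary outcome: at least 80% power for a 0.67 SD difference with 72 completers (80 x 0.9 = 72, or 36 per arm). A two-sample t-test with two-sided alpha 0.05 (assumed, as alpha is not stated) gives power 0.8005, so the figure reproduces. The present point does not depend on it.

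**Step 1: the components side by side.**

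| Source | Enrolment | Sessions completed |
|---|---|---|
| Protocol section 2, Aim 2a | yes (eligible patients enrolled) | yes |
| Protocol 9.1 and synopsis | yes, as an example | not named, not excluded |
| SAP 1.3 | yes, as the sole measure | absent |
| SAP 2.3.2 | yes (consented / approached) | absent |

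**Step 2: when the measure is settled.** Protocol 5.4 and SAP 1.1 place allocation after eligibility and consent. SAP 1.1 then continues: "obtains consent. All participants will then take a baseline survey and meet with the patient navigator". The sessions come later still. Each person's entry in the numerator or denominator is fixed before that person is allocated.

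**Step 3: what delivery can change.** Feasibility (SAP) = consented / approached. Protocol 5.1.1 plans 80 consented, but the number approached is not given. Assuming 100 to 267 approached, the result runs from 80/100 = 80% to 80/267 = 30%. Planned delivery is 40 people in Group A x 4 sessions = 160 sessions. The number of sessions delivered, from 0 to 160, does not enter the formula.

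**Step 4: whether the other primary measures fill the gap.** Satisfaction (SAP 1.3) is a nine-item rating of the relationship with the navigator. Acceptability (SAP 2.3.3) is a content analysis of exit interviews. Protocol 5.4 draws 20 interviewees equally from the two arms, so about 10 had been offered the HIEP. SAP 2.2 limits the analysis populations to people who completed both surveys and, for acceptability, the interview as well. People who left the programme may be under-represented. Neither measure counts sessions.

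**Step 5: whether completion could be estimated at this size.** Wilson 95% interval with n = 40 and z = 1.96:

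[p + z²/2n ± z·√(p(1−p)/n + z²/4n²)] / (1 + z²/n)

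- p = 32/40 = 0.80: (0.848 ± 0.133)/1.096 = 0.652 to 0.895, so 65 to 90%.
- p = 20/40 = 0.50: (0.548 ± 0.162)/1.096 = 0.352 to 0.648, so 35 to 65%.

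Both rates are assumptions, since the documents give no expected completion rate. They show that the planned arm size gives a usable estimate, and that two quite different outcomes would share one SAP feasibility figure.

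**The case against.** The strongest reply is that the SAP follows the protocol's analysis text. Section 9.1 and the synopsis name percent enrolled and nothing else, while sessions completed stands only in a parenthesis in the aims, with an undefined slash, no denominator and no threshold. This has weight. The narrowing begins in the protocol, and a reader who infers an undisclosed departure from the analysis plan goes further than the text allows: the SAP's claim to have followed that plan is defensible on this item. But an example does not cancel a component named in the aim. However the slash is read, sessions completed is part of Aim 2a.

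A reader might also infer that the whole primary outcome is fixed before anyone receives the HIEP. The documents do not support that. Acceptability and satisfaction are also listed as primary and are collected after the programme. Recruitment is rolling, so later consents follow earlier participants' sessions. The statement is true only of the feasibility percentage, and only participant by participant.

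Nor would the trial be silent on delivery. Sessions are recorded for fidelity (protocol 5.5), the follow-up survey is to ask about feasibility (5.5), and the Aim 3 interviews look for implementation barriers and navigators' concerns (9.2). These are useful context, but none is a completion count, and the SAP does not use the survey feasibility items.

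Finally, feasibility is descriptive and untested. The omission biases no estimate and leaves randomisation and the efficacy comparisons as they are. That stands and limits the severity.

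**Conclusion.** The point holds for the primary feasibility outcome. The SAP omits a component that Aim 2a names, and the measure it keeps carries no information on whether the four sessions were delivered: none of the 160 planned sessions can alter it. The other two primary measures do not replace the missing count.

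The conclusion rests on reading the slash in Aim 2a as joining two quantities, which is the natural reading, and on the SAP text from section 1.1 onward. The completion rates of 80% and 50% illustrate precision and do not measure an error. Grade: SHOULD-FIX. It is a completeness gap in a headline result of a pilot, cheap to close, with no effect on the randomised comparisons.

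**What to change.** In SAP 1.3 and 2.3.2, report feasibility as two measures:

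- (a) the enrolment percentage, as now;
- (b) session completion among all participants randomised to Group A: the distribution of sessions attended (0 to 4) and the percentage completing all four, with a 95% CI.

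Keep non-starters and those lost to follow-up in the denominator of (b). SAP 2.2 needs a sentence to allow this, because it now restricts analysis to people with both surveys. State what counts as an attended session. Take the count from navigator session records that include phone sessions: protocol 5.5 allows delivery by phone, but its recording sentence names only Zoom and in-person sessions.

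Interpret feasibility of the HIEP using both measures, and note the added one in SAP section 3.

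The cost is SAP wording and one descriptive table, plus a check that phone sessions were logged. No new visit or survey is needed. The downside is a feasibility statement that may be less favourable than the consent percentage alone.

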1.4 Sample Size Calculation

Sample size was calculated using the two mean sample test in STATA 14. The study should have at least 80% power to detect differences in the mean improvement in the COST score between the intervention and control groups which differ by 0.67 SD based for our target of N=72 completion.

1.5 Study Procedures

At the beginning of the study, all participants will consent to participation. The consent document has been reviewed and approved by the University of Utah IRB. All research will be completed in the timeline outlined in the study protocol.

All participants will be given a baseline survey on the REDCap platform, asking questions about basic, demographic, information, financial toxicity, and participant's knowledge and comfortability using insurance. All participants will meet with the patient navigator to determine other needs that may need to be met and will be connected with appropriate resources. Individuals who do not participate in the intervention will have access to this navigator throughout the course of the study, as part of their usual standard of care. Individuals who participate in the intervention will meet with the patient navigator four times for 30-minute biweekly insurance education sessions. Five months after the baseline survey is complete all participants will be given a follow up survey, asking the same questions asked at baseline.

A random group of participants in both the intervention and non-intervention group will be invited to participate in an end-of-project interview.

2. Statistical Methodology

2.1 Statistical Variables

2.1.1 Background and demographic characteristics

Basic demographic characteristics such as race, age and gender will be collected as well as background information on participant's cancer diagnosis such as age at diagnosis, type of insurance at diagnosis will be collected.

2.1.2 Efficacy

Our efficacy measures will be collected at both baseline and follow-up as this study is interested in examining the change between the two timepoints. These measures include 9 items on confidence using and being proactive with insurance selected from the Health Insurance Literacy Measure (HILM) and 7 items on familiarity with insurance protections under the Affordable Care Act (ACA). For each of these measures, we summed each item to evaluate overall mean differences from baseline to follow-up, with higher scores identifying higher knowledge or confidence. Financial hardship related to cancer was assessed by the COmprehensive Score for financial Toxicity (COST) which consists 11 items that cover worries about out-of-pocket costs, with lower scores indicating greater toxicity.

2.2 Statistical Analysis Population

The analysis populations include all participants who completed both the baseline and the follow-up survey. For the acceptability analysis individuals must have also complete the interview at study close.

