5.1 Recruitment/Participant Identification Process

5.1.1 Enrollment Goals

1. Aim 2: 6-7 participants per month, for a total of 80 participants. N=40 HIEEnhanced care, intervention (Group A), N=40 for usual care (Group B), stratified by age and treatment site and randomized to study arm (Group A or B) N=40 18-26 year-olds, N=40 27-40 year-olds.
2. Aim 3: Have 20 participants from Group A and B participate in study interviews, stratified by age. N=10 18-26 year-olds, N=10 27-40 year-olds

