2.4.2 Missing data

Missing demographic information was supplemented using participant medical records.

For efficacy analyses, individuals missing any of the questions used to calculate the associated sums of questions were dropped from analysis.

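### The efficacy comparison is a complete-case analysis by assigned arm, with no all-randomised set and no missing-outcome sensitivity analysis

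*SAP*

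**What the plan says.** SAP 2.2 sets the population: "The analysis populations include all participants who completed both the baseline and the follow-up survey". It adds a further condition (the exit interview) for acceptability only, so this sentence governs efficacy.

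Both surveys follow allocation. SAP 1.1 has computer-generated allocations "automatically assign individuals to a study arm after the study coordinator determines patients' eligibility and obtains consent", and continues: "All participants will then take a baseline survey and meet with the patient navigator".

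SAP 2.4.2 adds an item-level exclusion for efficacy: "individuals missing any of the questions used to calculate the associated sums of questions were dropped from analysis". SAP 2.1.2 lists 9 HILM items, 7 ACA items and 11 COST items, so the analysed set can differ from one outcome to the next.

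SAP 2.3.5 specifies t-tests on change and linear regression by treatment group. SAP 2.4.2 fills gaps in demographic data from medical records but does nothing similar for outcomes. The sensitivity analyses named in SAP section 3 concern policy-holder status and recruitment site.

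On expected loss, Protocol 9.1 says: "We expect at least 72 to complete the 3 month follow-up (10% attrition rate) based on retention in our previous studies".

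**The concern.** Randomisation makes the two arms comparable as allocated. To be analysed here, a person must return a baseline survey, return a follow-up survey and answer every item of the score, and all three happen after allocation. If the people who fail a condition differ between arms, in number or in how their scores would have changed, the arms are no longer comparable and the between-arm difference absorbs that selection.

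Loss could plausibly differ by arm. Only Group A is asked to attend four extra sessions. Protocol 5.5 times Group A's follow-up from the end of the program and Group B's from baseline, whereas SAP 1.5 uses five months after baseline for everyone. Under the protocol wording, the follow-up date is undefined for a Group A participant who never finishes the sessions.

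At stake is the secondary efficacy estimate, which readers will take as a randomised comparison. The primary outcomes are not affected in this way: SAP 2.3.2, for example, counts feasibility among people approached.

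**Working it through.** **Inputs.** 40 per arm, 80 in total (Protocol 5.1.1). 10% attrition, 72 completers (Protocol 9.1). A difference in mean COST improvement of 0.67 SD with 72 completers and at least 80% power (SAP 1.4). Alpha and sidedness are not stated; 0.05 two-sided is assumed. The synopsis and Protocol section 3 give 120 and 150; 80 is used because the power statement rests on it.

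**The plan's own figure.** 80 × 0.90 = 72, or 36 per arm if loss is equal. A two-sample test at 0.67 SD has power 80.05% (t) or 81.1% (normal). The stated power reproduces and already allows for the 8 losses. It has almost no reserve for item-level exclusions among the 72: power (t) is 77.7% at 34 per arm and 75.1% at 32.

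**Bias in general.** Let dA and dB be the fractions lost, and gA and gB the completer mean change minus the non-completer mean change, in SD. Then

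completer difference − all-randomised difference = dA·gA − dB·gB.

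This is zero if loss and gap match across arms. It is negative if the loss falls mainly in Group B and gB is positive: with dA = 0, dB = 0.20 and gB = 0.5, the completer analysis understates the difference by 0.10 SD.

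**Illustration.** Assume 8 losses, a completer effect of 0.67 SD, Group A leavers with no benefit over controls (gA = 0.67), and Group B leavers like Group B completers (gB = 0). Then

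all-randomised effect = 0.67 × (40 − losses in A)/40, and overstatement = 40/(40 − losses in A) − 1.

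| Losses A/B | All-randomised effect (SD) | Overstatement |
|---|---|---|
| 0/8 | 0.67 | 0% |
| 2/6 | 0.64 | 5% |
| 4/4 | 0.60 | 11% |
| 6/2 | 0.57 | 18% |
| 8/0 | 0.54 | 25% |

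**A range for the gap.** Keep gB = 0 and let gA run from 0.25 to 1.0 SD. At 10% loss per arm the bias is 0.10 × gA = 0.025 to 0.10 SD, or 4% to 15% of 0.67. At 20% loss in A and none in B it is 0.05 to 0.20 SD, or 7% to 30% of 0.67. At the top of each range, with no true effect among all randomised, the two-sided 5% error becomes about 7.0% (0.10 SD, 36:36) and 13.2% (0.20 SD, 32:40).

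**Would a missing-at-random method remove it?** Not in this illustration. Imputation from arm and baseline, or a mixed model on two time points, fills in a leaver from similar completers in the same arm. If Group A leavers in truth gain no benefit, both still return about 0.67 SD. Only an analysis that departs from missing at random shows the lower figures.

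**The case against.** The strongest reply is that this is ordinary complete-case analysis in a pilot. Participants are compared in their assigned arm, planned loss is 10%, and efficacy is secondary. Follow-up is separated from attendance: both arms get the same reminders (Protocol 5.5) and a separate $20 gift card for the follow-up survey (Protocol section 8). Protocol 9.1 also allows models with random effects for patient, which can use partial data, and SAP section 3 says the protocol analysis was followed. Much of this stands and limits the weight of the point. The random-effects option, however, is only optional and does not appear in SAP 2.3.5, and nothing in either document handles missing outcomes.

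Four stronger readings are tempting but unsupported:

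- *The estimate describes only people who finished the HIEP.* SAP 2.2 requires surveys, not sessions. A Group A participant who attends nothing but returns both complete surveys stays in Group A.
- *Those who disengage from the sessions are the ones who miss the survey, so the bias is upward.* Neither document says so. It is an assumption, and the direction is open.
- *The overstatement is at least 11%.* That is the equal-loss case under one assumption. The same formula gives 5% at 2/6 and 0% at 0/8.
- *An inflated effect will size the larger trial.* Aim 3 refines the program through interviews. Neither document says the effect estimate will be carried forward.

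**Conclusion.** The point holds as a matter of validity, with modest weight. SAP 2.2 and 2.4.2 together condition the efficacy comparison on three post-randomisation events, and no planned analysis shows how far the result depends on them. Bias is possible, not certain.

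Under the illustration the overstatement is 0% to 25%, and 11% at equal 10% loss. This rests on three assumptions: 0.67 SD, which is the plan's detectable difference and not a forecast, is taken as the effect in completers; Group A leavers have no benefit over controls; and Group B leavers resemble Group B completers. Other patterns give zero or a bias in the opposite direction. There is no sample-size error, since the power statement is already based on 72 completers.

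**What to change.** - **SAP 2.2:** define the efficacy set as all randomised participants in their assigned arm. Keep the both-surveys set as a supportive analysis.
- **SAP 2.4.2:** replace the rule that drops a person for one missing item with multiple imputation of items and scores, using arm, age stratum, site and whatever baseline data exist. Include participants randomised without a baseline score.
- **Sensitivity analysis:** because imputation or a mixed model assumes missing at random, add a missing-not-at-random analysis. Either give Group A non-completers no benefit over controls, or apply a range of shifts separately by arm. With losses by arm, this is the part that addresses the bias illustrated here.
- **Reporting:** give losses by arm, with reasons, separately for a missing baseline survey, a missing follow-up survey and missing items.
- **Timing:** reconcile the follow-up date in Protocol 5.5 with SAP 1.5, so that it is defined for Group A participants who do not finish the sessions.

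The cost is SAP wording and a little more analysis, with no new data. The estimate may become smaller or less precise. Full recovery of all 80 outcomes would raise power for 0.67 SD to 84.1% (t), but that is a ceiling imputation will not reach. Parts of the SAP are in the past tense; if analysis has begun, the same additions can be made and labelled as added later.
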